In order to obtain 30 study completers (~10-15% expected attrition rate), 35 medication-free, medically-stable and otherwise psychiatrically healthy adults (25-55 yrs) with 1) current MDD per DSM-V criteria, 2) plasma CRP >2 mg/L, and 3) score ≥ 5 on an anhedonia subscale of the Inventory of Depressive Symptomatology-Self-Report (IDS-SR), will be randomized to two study tracks (A and B) to receive both placebo and L-DOPA (starting dose of 150 mg/day with dose escalation 150 mg/day per week to a final dose of 450 mg/day) in a 6-week, double-blind, placebo-controlled, crossover study (see **Figure 1**). Patients will undergo resting-state functional magnetic resonance imaging (fMRI) at baseline, after 1-week of placebo, and after 1-week at each dose of L-DOPA to establish target engagement in the brain for L-DOPA versus placebo to improve FC in reward circuitry. Symptoms of anhedonia and an objective measure of motivation will be assessed as preliminary data regarding L-DOPA effects on behavior in relation to change in FC. Additional behavioral, biologic and MRI measures will be collected at baseline for use as predictors of response and to enhance interpretation of results. Safety and tolerability and data on the effect of L-DOPA on anhedonia and motivation in relation to target engagement in the brain (FC) will also be assessed.

Aim 1: To determine whether L-DOPA increases VS-vmPFC functional connectivity in MDD patients with high CRP (>2 mg/L) and anhedonia.

Hypothesis 1: L-DOPA versus placebo will increase VS-vmPFC FC along with plasma L-DOPA levels, and with maximal effects at higher doses.

Exploratory aims: To obtain information on the dosing and tolerability of L-DOPA in our patient population, while collecting preliminary data on whether L-DOPA-sensitive fMRI FC brain biomarkers are affected in association with improvement in anhedonia and motivation.

Exploratory hypotheses: L-DOPA will be well-tolerated in otherwise medically-stable MDD adults with CRP >2mg/L and anhedonia at all doses tested, and improvement in FC in reward circuitry will occur in association with improved motivation and motor slowing.

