
4.0 Study Endpoints *

Milestone for R61: Target Engagement of Brain. Targeted VS-vmPFC connectivity will serve as the primary outcome and will be assessed for determining the Go/No-Go Criteria. Targeted FC for each subject and treatment condition will be calculated as the degree of correlation in activity between a 3mm³ radius sphere in VS^{27,65} and the vmPFC ROI identified as being reward-sensitive in neuroimaging meta-analyses¹⁰⁵ (MNI coordinates x=0, y=44, z=-8, cluster size=1408 mm³ and encompassing parts of BA11 and ventral BA32 of ACC) or other similar ROIs used to define vmPFC in our previous work.^{27,64,65,106} This method will ensure rigor and reproducibility and application of results to potential future trials because the seeds and ROI are predefined, as opposed to those derived from whole-brain and data-driven analyses which are determined based on the specific patient sample. Z-scores will be extracted and the change in mean FC values after each dose of L-DOPA or placebo compared to baseline will be calculated.

FC between bilateral VS seeds and the vmPFC ROI will be examined separately and change in FC in either the right or left VS can contribute to meeting the Go/No-Go criteria. However, based on our previous work in MDD and IFN- α -induced depression^{21,27} and our preliminary studies, we anticipate that this change will be more pronounced on the left side. Response may also be strongest in subjects with greatest bioavailability of L-DOPA. If more than 1 dose of L-DOPA meets criteria, % of patients and mean number of reported side effects will be compared across doses to determine the effective dose that was most tolerated by patients. If doses are similarly tolerated, % change in behavior (EEfRT > anhedonia) will be used. Statistical significance, ES or sensitivity analyses may be used to assist with selection of the optimal dose.

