Additional Analyses for Publication and Dissemination: Brain Target- Targeted FC Z scores (as described above) will be entered into linear regression models including clinical covariates (see below) and both conservative (Bonferroni) and powerful (Fisher LSD) post-hoc analyses to assess change in FC across the 3 doses of L-DOPA compared to placebo and to each other. Linear models will also be used to determine whether FC increases as a function of increasing plasma L-DOPA, and whether patients with low bioavailability exhibit low Δ FC. In addition to the targeted FC that will be used to assess Go/No-Go criteria, hypothesis-driven and data-driven whole-brain analysis will also be explored and compared before and after L-DOPA and placebo. Consistent with our previous data, these analyses will include VS seed-to-voxel-wise comparisons of L-DOPA versus placebo, as well as network analyses using GBC and PBNA, as a secondary outcome measure and to identify other circuits that may be affected by L-DOPA. For all analyses, concentration of CRP and final dose will be explored as a linear predictor of response to L-DOPA. Clinical covariates such as age, sex, race, BMI and ATQR and/or bipolarity scores will be explored as potential confounders or moderators of L-DOPA effects on FC. **Integration of Brain and Behavior:** As described for FC, linear regression models and post-hoc analyses will be used to assess change in behavioral outcomes across the 3 doses of L-DOPA compared to baseline, to placebo and to each other, and whether response was modified by plasma bioavailability of L-DOPA, CRP, cytokine or sex hormone concentrations, or clinical covariates. Random intercept linear mixed models will be used to assess whether change in FC predicts change in anhedonia and motivation and in relation to clinical covariates. Overall depression scores and SHAPS-C and MAP-SR will be explored as secondary outcomes. Summary scores for dose-response (e.g. AUC) may be used to assess relationships among variables.

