(3) The patient has not informed study staff or the psychiatric clinician of any condition that, in the opinion of the PI or PI's designee, would make the patient unsuitable for or unable to complete further screening

Following the in-person screening visits and Pre-Baseline data collection, the patient will undergo the Baseline visit including MRI scan and randomization. At the Baseline visit, urine will be obtained for toxicology and pregnancy testing (where appropriate) and a fMRI scan will be performed. Subjects will receive standardized clinician-administered interviews and ratings for psychiatric symptoms, will be asked to fill out self-report questionnaires and will undergo objective tests of motivation and motor activity. Blood will also be drawn for the measurement of inflammatory marker/hormone levels after the scan procedures, and patients will receive study medication. At the end of each indicated week of treatment (7 days after each dose change in weeks 1, 3, 4 and 6), subjects will undergo fMRI scans, receive standardized clinician-administered interviews and ratings for psychiatric symptoms, will be asked to fill out self-report questionnaires, have blood drawn for L-DOPA concentrations and inflammatory markers, urine will be obtained for toxicology, and pregnancy testing, and will perform objective tests of motivation/motor activity. Safety and tolerability will also be assessed. For follow up visits at weeks 2 and 5, patients will either be seen in person (where possible) or virtually to fill out self-report questionnaires, height, weight and vital signs will be recorded (in-person only), update psychiatric symptoms, and safety and tolerability will be assessed. If the visit occurs virtually, medication will be mailed to the participant and unused medication will be returned at the next in-person visit.

Table 2. Schedule of Study Procedures and Assessments.

| Assessments | Intake/ Consent | Screen A | Screen B- (Incl. Pre- Baseline Assess.) | Baseline | Weeks 1, 3, 4, 6 | Weeks 2 & 5 |
|--|--------------------|----------|--|----------|---------------------|----------------|
| Consent, Intake Registration Form, PHQ-9 [Intake or Screen A, optional at Screen B], Med-Psych Prescreen Form, History of Chronic Conditions, Medication Avoidance List* | X | [X] | [X] | | | |
| SCID V-modified (Mood, Anxiety, PTSD modules), Bipolarity index, ATRQ, Clinical Review for Screening** | X | [X] | [X] | | | |

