12.0 Local Number of Participants

12.1 Seventy medically-stable male and female subjects between the ages of 25 and 55 will be enrolled in this study in order to obtain 35 qualified subjects to be randomized for the R61 study.

12.2 Thus, n=70 will be enrolled for screening, and n=35 will be randomized in order to obtain and analyze data from n=30 study completers when considering a ~10-15% attrition rate.

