Sample size was estimated to have adequate power to observe statistical significance based on our preliminary data and the proposed Go/No-Go criteria described above (see **Power Analysis** section for detail). For the R61 Phase, the proposed threshold criteria for the primary outcome of target engagement in the brain (VS-vmPFC FC) is a mean change with L-DOPA from baseline of $\geq 20\%$ greater than that of placebo. Based on the means and standard deviations from our previous work, a $\geq 20\%$ difference in mean change in FC corresponds to a effect size (ES) of 0.65, indicating that with a 2-sided alpha=5%, a total of 30 patients (out of 35 that will be studied to account for potential drop-outs) will be required to have $>90\%$ power for statistical analysis (see **Figure 1** in the **Power Analysis** section of **Human Subjects** for detail). Based on our preliminary data on the relationship between change in EEfRT performance and change in VS-vmPFC FC after acute L-DOPA of $r=0.6$, we will have also have $>95\%$ power to detect correlations between change in FC and improvements in motivation, a secondary outcome to be explored.

Statistical Analysis

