Brain Target- Targeted FC Z scores (as described above) will be entered into linear regression models including clinical covariates and both conservative (Bonferroni) and powerful (Fisher LSD) post-hoc analyses to assess change in FC across the 4 doses of L-DOPA compared to baseline, placebo and to each other. Linear models will also be used to determine whether FC increases as a function of increasing plasma L-DOPA, and whether patients with low bioavailability exhibit low FC. Treatment resistance (as measured by ≥ 2 on the MGH-ATRQ) will also be assessed in linear models to determine whether it is associated with greater response to L-DOPA. In addition to the targeted FC that will be used to assess Go/No-Go criteria, hypothesis-driven and data-driven whole-brain analysis will also be explored and compared before and after L-DOPA. Consistent with our previous data, these analyses will include VS seed-to-voxel-wise comparisons of L-DOPA versus placebo, as well as network analyses using GBC and PBNA, as a secondary outcome measures and to identify other circuits that may be affected by L-DOPA. For all analysis, concentration of CRP and final dose will be explored as a linear predictor of response to L-DOPA. Clinical covariates such as age, sex, race and BMI will also be explored as potential confounders or mediators of L-DOPA effects on FC. As described for FC, linear regression models and post-hoc analyses will be used to assess change in behavioral outcomes across the 3 doses of L-DOPA compared to baseline, placebo and to each other, and whether response was modified by plasma bioavailability of L-DOPA, CRP or cytokines concentrations or clinical covariates. Overall depression scores, SHAPS-C and MAP-SR will also be explored as an outcome. Integration of Brain and Behavior: Random intercept linear mixed models will be used to assess whether change in FC predicts change in anhedonia and motivation and in relation to clinical covariates. Overall depression scores and motor behaviors will also be explored as outcomes. Summary scores for dose-response (e.g. area under the curve) may be used to assess relationships among variables.

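### The planned brain–behaviour mixed model gives one slope that mixes within-patient and between-patient association, and the plan does not say which is meant

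*Combined protocol and SAP*

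**What the plan says.** Section 4.0 (Integration of Brain and Behavior) states "Random intercept linear mixed models will be used to assess whether change in FC predicts change in anhedonia and motivation", in relation to clinical covariates. Section 17.1 repeats the sentence.

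The predictor is defined in Section 4.0: "the change in mean FC values after each dose of L-DOPA or placebo compared to baseline will be calculated". Scans and behavioural tests come "7 days after each dose change in weeks 1, 3, 4 and 6" (Section 6.1), so a completer has four changes in FC and four in behaviour, all measured against the same baseline visit. Section 12.2 plans that "n=35 will be randomized in order to obtain and analyze data from n=30 study completers".

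The exploratory hypothesis in Section 2.0 is that "improvement in FC in reward circuitry will occur in association with improved motivation and motor slowing". It does not say whether this means across patients or within a patient across conditions.

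For this model the documents mention no centring, patient-mean term, or term for condition, dose, week or track. Section 17.1 gives one power statement for the brain–behaviour link: a correlation of 0.6 with 30 patients, for power above 95%. Both sections also allow a per-patient dose-response summary such as AUC as an option. The analysis sits among the additional analyses for publication, outside the Go/No-Go milestone.

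**The concern.** Two different questions can be put to these data:

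- **Between patients:** do patients whose FC rises more overall also improve more overall?
- **Within a patient:** is behaviour better in the condition where that patient's FC is higher?

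A random intercept allows for correlation among a patient's outcomes. It does not separate the two associations carried by a predictor that varies both between and within patients. A single coefficient on change in FC averages them, with weights set by the variance components.

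A significant slope could therefore be read as FC and behaviour moving together within patients when it reflects only differences between patients. Conversely, a real between-patient link could be diluted and missed. What is at stake is the interpretation of the exploratory hypothesis.

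**Working it through.** **The plan's own figure.** Power for r = 0.6 with n = 30, by Fisher z: Φ(atanh(0.6)·√27 − 1.96) = Φ(0.693 × 5.196 − 1.96) = Φ(1.64) = 0.950. A simulated t-test of r gives 0.955. The stated figure reproduces. It treats each patient as one pair, so it is power for a between-patient correlation and not for the mixed model. Two-sided 5% is stated for the primary outcome and is assumed here.

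**Why the slope is a blend.** With T changes per patient, the random-intercept slope is approximately

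b = (w_W·b_W + w_B·b_B) / (w_W + w_B),

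where w_W = (T − 1) × within variance of x / within residual variance, and w_B = variance of the patient means of x / residual variance of the patient means of y.

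Take T = 4, no within link (b_W = 0), between-patient r = 0.6 and ICC 0.5 for both changes (assumed, total variance 1):

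- Variance of patient means = 0.5 + 0.5/4 = 0.625; covariance = 0.6 × 0.5 = 0.30; b_B = 0.30/0.625 = 0.48.
- At b = 0.132, residual variance of patient means = 0.625 − 2(0.132)(0.30) + 0.132²(0.625) = 0.557; within residual = 0.5(1 + 0.132²) = 0.509.
- w_B = 0.625/0.557 = 1.12; w_W = 3 × 0.5/0.509 = 2.95.
- b = 1.12 × 0.48/(1.12 + 2.95) = 0.132, which is self-consistent.

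The single slope is neither 0 (within) nor 0.48 (between). The simulated mean was 0.129.

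**Rejection rates.** 30 patients × 4 changes, true within slope 0, REML, two-sided 5%, 2,000 runs per row. The between-patient r and ICC are assumptions.

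| r | ICC | Single slope, mean | Single slope p<0.05 | Within term p<0.05 | Patient-mean term p<0.05 |
|---|---|---|---|---|---|
| 0 | 0.2 | 0.00 | 4.6% | 4.8% | 5.0% |
| 0 | 0.5 | 0.00 | 5.0% | 4.9% | 4.4% |
| 0 | 0.7 | 0.00 | 6.6% | 5.9% | 4.4% |
| 0.3 | 0.2 | 0.04 | 6.6% | 5.3% | 13.0% |
| 0.3 | 0.5 | 0.06 | 11.1% | 5.6% | 25.4% |
| 0.3 | 0.7 | 0.07 | 11.8% | 5.2% | 31.4% |
| 0.6 | 0.2 | 0.07 | 12.3% | 4.3% | 34.2% |
| 0.6 | 0.5 | 0.13 | 31.1% | 5.9% | 78.7% |
| 0.6 | 0.7 | 0.15 | 41.5% | 5.4% | 90.4% |

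A separate simulation at r = 0.6 and ICC 0.5–0.7 gave 26–30% for the single slope, about 4.5% for the within term and 86–96% for the patient-mean term. The exact percentages depend on the set-up; the ordering does not.

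**Where a between-patient correlation of changes could come from** (raw scores simulated, then change from baseline taken):

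- Stable trait levels of FC and behaviour correlated 0.6: single slope significant in 5.5%. Subtracting baseline removes this source.
- Patient-level response correlated 0.6: 6.2% if the SD of response is half the visit-to-visit SD, 10.8% if equal to it.
- Correlation of 0.6 confined to the baseline-visit values, which enter every change: 32%.

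**Effect of treatment itself.** Let the three active conditions shift mean FC and mean behaviour together by 0.5 or 1 SD, with no individual-level link and ICC 0.5:

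| Model | 0.5 SD | 1 SD |
|---|---|---|
| Single slope, no condition term | 15% | 84% |
| Within term, no condition term | 18% | 91% |
| Within term with week and track only (placebo scan assumed first in one track, last in the other) | 10–11% | 67–69% |
| Within term with condition | about 5% | about 5% |

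Splitting the predictor is therefore not sufficient without a condition term.

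**The case against.** The strongest reply is that the sponsor may want the between-patient link. The hypothesis speaks only of association, the one power figure is for a between-patient correlation, and the optional AUC summary is one value per patient. A simulation with a between-patient r of 0.6 then contains the effect the plan hopes to find, and a significant slope is no false positive. This stands against any claim that the hypothesis is within-patient; the documents do not say so. It does not rescue the single slope. On that reading it finds the link in 31–42% of trials at ICC 0.5–0.7, where a separate patient-mean term finds it in 79–90%.

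A reader might also infer that the plan has chosen an uncentred predictor. It has not; it is silent, and entering change in FC as calculated is simply the plain reading.

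A reader might further infer that any stable trait confounds the slope. Change from baseline removes additive trait levels, as the 5.5% result shows. What remains is factors that drive response, some of which the plan itself names (L-DOPA bioavailability, CRP, cytokines), and shared baseline-visit noise. Exploring clinical covariates may reduce the first but is not aimed at the second.

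Finally, the inflation is small at r = 0.3 and absent at r = 0. That is correct and belongs in the conclusion.

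**Conclusion.** The concern holds as a gap in specification. As written, the model yields one slope that blends two associations, and the plan neither says which is the target nor includes the terms to separate them. With no within-patient link, the slope is significant in about 5% of trials at a between-patient r of 0, 7–12% at 0.3 and 12–42% at 0.6, for ICCs of 0.2–0.7. The r and ICC values and the treatment shifts are assumptions for this model; the documents supply none.

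It would be going too far to say that the crossover's advantage is lost or that the case for the R33 is undermined. The L-DOPA versus placebo comparisons do not use this model. Go/No-Go rests on FC, and behaviour enters dose selection only through its percent change when tolerability is similar. Sample size, alpha and the milestone are unaffected. This is a worthwhile, low-cost improvement to an exploratory analysis.

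**What to change.** In Sections 4.0 and 17.1, specify for EEfRT, IDS-SR anhedonia and the motor outcomes:

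1. Replace the single FC term by two: the patient's mean change in FC, and the deviation of each change from that mean.
2. Add condition/dose, week and track, keeping the random intercept and planned covariates.
3. Report both slopes, and state in advance which one tests the exploratory hypothesis.

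**Cost.** No new data. Taking condition and week as four-level factors, the added terms are one for the patient mean, three for condition, three for week and one for track: eight, against 30 × 4 = 120 change scores. Before finalising, confirm from the track layout that condition, week and track can be estimated together.

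One trade-off should be stated. Once condition is in the model, the within slope no longer includes association carried purely by the mean treatment effect. The version without the condition term can be shown as a labelled secondary result.

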5.0 Study Intervention/Investigational Agent

Description: Carbidopa-levodopa (Sinemet) is a combination of two drugs, L-DOPA and carbidopa. Carbidopa-levodopa is used primarily in the treatment of Parkinson's disease (although it is also FDA approved for other movement disorders such as Restless Legs Syndrome). Parkinson's disease is believed to be caused by low levels of dopamine in certain parts of the brain. When L-DOPA is taken orally, it crosses into the brain through the "blood- brain barrier." Once it crosses, it is converted to dopamine. The resulting increase in brain dopamine concentrations is believed to modulate nerve conduction and improve movement impairments. Carbidopa does not cross the blood-brain barrier. Carbidopa is added to L-DOPA to prevent its breakdown before crossing into the brain. The addition of carbidopa allows lower doses of L-DOPA to be used. This reduces the risk of side effects from L-DOPA such as nausea and vomiting. Nausea and vomiting are frequent side-effects of taking levodopa, and often improve with increasing time on medication. This combination medicine was approved by the FDA in 1988. Carbidopa-levodopa is taken several times per day for treatment of Parkinson's disease, up to 800 mg daily. Patients in this study will receive L-DOPA at doses ranging from 150 to 450 mg administered with at a ratio of 1 mg carbidopa for every 4 mg L-DOPA. Our preliminary data using

acute administration of 250 mg L-DOPA to MDD patients with CRP >2mg/L increased corticostriatal FC in reward circuitry as measured by fMRI (the primary study outcome) without only mild adverse events that are anticipated during initial exposure to the medication, primarily nausea (with vomiting in some patients). Other common symptoms that were experienced included headache and drowsiness or lightheadedness. Furthermore, in a similar recent study in aged adults with depression (>/=60 years),³⁰ L-DOPA administered at the same doses proposed herein (also 1 week at each dose) decreased depressive symptoms and was well-tolerated. Indeed, the percent of patients reporting nausea (the most common symptom) decreased from 19.4% in Week 1 to 9.1% in Week 3, despite dose increases by 150 mg/week. Symptoms of headache and drowsiness occurred in less than 10% of patients throughout the duration of the study, and insomnia occurred in 8% in the first week which decreased to 3% in week 3. Moreover, patients were monitored for dyskinesias (a common symptom in Parkinson's Disease that may be specific to neurodegenerative disease pathology) and scores were 0.0 at Week 3 for all subjects.

Table 1. Expected Frequency and Duration of Common Anticipate Mild Adverse Events Associated with L-DOPA

| Anticipated Mild Adverse Events Associated with L-DOPA | Approximate Expected Frequency | Anticipated Expected Duration |
|--|----------------------------------|---|
| Nausea (may include vomiting in some patients) | 20-30% 10-20% ~10% or less | First few days First few weeks After week 3 |
| Insomnia | ~10% ~5% or less | First week After the first week |
| Headache | ~5-10% | Anytime during treatment |
| Lightheadedness, dizziness or drowsiness | ~5-10% | Anytime during treatment |

The following rare but serious side effects have also been reported following the use of chronic high doses of L-DOPA for treatment of Parkinson's disease: easy bleeding/bruising, signs of infection (e.g., fever, persistent sore throat), tingling of the hands/feet, vision changes (e.g., blurred/double vision), chest pain, seizures, vomit that looks like coffee grounds, black/tarry stools, unusual muscle stiffness, severe confusion, sweating, fast/irregular heartbeat, rapid breath or trouble breathing, painful or prolonged erection in males, rash, itching/swelling (especially of the face/tongue/throat), and severe dizziness. Transient and mild side effects that may occur following acute administration of the doses used in this study include: dizziness, nausea, vomiting, increased sleepiness or trouble sleeping, and headache. L-DOPA may also increased eye blinking/twitching, cause fainting, mental/mood changes, and worsening of involuntary movements/spasms.

5.1 Drug/Device Handling: L-DOPA and placebo will be dispensed to by Emory Investigational Drug Services (IDS) under an IDS-SOP and delivered to the principal investigator or study team member. The principal investigator or

health care providers on his/her research team will provide the medicine to the subjects. To maintain blinding during dose escalation and across tracks, study medication will be dispensed to each participant at their weekly follow-up visits. In order to assist participants and the monitoring of adherence, medication will be dispensed in blister packs and all unused medication will be returned to the pharmacy. Compliance will be monitored and recorded. Falling below 85% compliance on more than one week may be grounds for dismissal.

5.2 N/A. Investigator Justification for IND Exemption is attached.

